3. PROTOCOL SYNOPSIS

Title	A Phase I/II, Open Label Study of Ad-RTS-hIL-12, an Adenovirus Vector Engineered to Express hIL-12, in Combination with an Oral Activator Ligand, in Subjects with Unresectable Stage III or IV Melanoma
Protocol Number	ATI001-101
Study Sponsor	ZIOPHARM Oncology, Inc.
Objectives	
The primary objective is to:
 
• Evaluate the safety and tolerability of intratumoral injections of INXN-2001 (Ad-RTS-hIL-12) in combination with INXN-1001 (activator ligand) in subjects with unresectable Stage III or IV melanoma. 
The secondary objectives are to:
 
• Inform the selection of an INXN-1001 dose(s) and regimen for further study in combination with INXN-2001.• Assess preliminary anti-tumor activity according to RECIST 1.1 criteria.• Assess anti-tumor response based on total measurable tumor burden.• Evaluate the immunological effect of study treatment in terms of cellular and humoral immune responses, as well as other biological activities in the injected tumor(s), tumor-involved draining lymph nodes (if accessible) and in the peripheral circulation.• Evaluate the extent of the uptake of INXN-2001 into tumor cells and tumor-infiltrating immune cells, and to assess adenovirus vector shedding in body fluids.• Assess the pharmacokinetics (PK) of INXN-1001 in subjects with unresectable stage III or IV melanoma.
Clinical Phase	I/II
Study Drugs	INXN-2001 (Ad-RTS-hIL-12) INXN-1001 (Oral Activator Ligand) Concurrent INXN-2001 and INXN-1001 dosing will be referred to as “study treatment” throughout this protocol.
No. of Subjects	Approximately 30 subjects (3 subjects per dose level cohort in Phase I and approximately 15 subjects enrolled in Phase II at a single dose level at or below the MTD), exclusive of replacement subjects or the addition of intermediate dose level cohorts, if any.
Number of Centers	Multi-center (approximately 8 to 12 centers)

Study Design	Single-arm, open label, Phase I/II dose escalation study of intratumoral injections INXN-2001 and oral INXN-1001 in subjects with unresectable Stage III or IV melanoma.											
Table 1: Study Design												

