6.2.4 Definition and Management of Dose-Limiting Toxicity (DLT)

Dose-limiting toxicity (DLT) is defined as:

- Any injection site reaction that includes ulceration, necrosis, severe tissue damage or where operative intervention is required.
- Any local or systemic injection reaction that has life-threatening consequences, requires urgent intervention or results in death.

- Any study drug-related \geq Grade 3 adverse event, except nausea and/or vomiting in subjects who did not receive optimal treatment with anti-emetics.

Phase I and Phase II, Group 1: If DLTs have been observed in >1 of the 3-6 subjects in a cohort during the first treatment cycle, the MTD will have been exceeded and further use of that dose will be discontinued in all subjects, and the next lower dose cohort will be assessed as to whether it meets the definition of the MTD.

Phase II, Group 2: If an adverse event that meets the Phase I DLT definition is observed in >1 of the 3-6 subjects in Group 2 during the first treatment cycle, the SRC will convene to discuss reduction in dose and/or change to posology and the cohort will be expanded by 3 subjects. The recommended Phase II dose will be the dosage and posology where ≤ 1 of 3 to 6 subjects experiences an adverse event as described in the definition of DLT.

The Medical Monitor should be immediately notified of any potential DLT. Subjects will be withdrawn from study treatment if they experience an injection site reaction that meets DLT criteria or other Grade 3 toxicity related to study drug that, upon review of the SRC, is deemed to be a DLT. If, however, the subject has experienced a substantial benefit from treatment and the SRC recommends continuation on the study, re-exposure to the experimental treatment may proceed at a lower dose of INXN-1001 on a case by case basis. Any subject who experiences a Grade 4 toxicity related to study treatment will be withdrawn from study.

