7.4 REPLACEMENT OF SUBJECTS

Subjects who are withdrawn from study treatment prior to completing Cycle 1 dosing for reasons other than toxicity may be replaced so that a full cohort of subjects completes Cycle 1 safety evaluations. In addition, should a subject discontinue study treatment before receiving 3 cycles for reasons other than toxicity, another subject may be added to that dose cohort so as to result in a total of at least three subjects for full analysis.

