8.0 Analysis Populations

The target population for this study is adult patients with unresectable Stage III or IV melanoma for which there is no alternative curative therapy.

For the analysis, two populations will be used: a Safety population (SAF) and an Activity Evaluable population (ACEV).

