8.1 Safety Population (SAF)

The Safety population is defined as all patients who receive at least one INXN-1001 capsule or, in the event an injection of INXN-2001 is administered before an INXN-1001 capsule is taken, at least one injection of INXN-2001.

The safety population will be used for the analysis of safety data based on the actual initial dose of INXN-1001 received.

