12.0 Safety Endpoints

Safety will be assessed from records of AEs, laboratory values (clinical chemistry, hematology and urinalysis), vital signs, 12-Lead electrocardiogram (ECG) and results of physical examination. Severity of adverse events as determined by NCI Common Terminology Criteria for Adverse Events (CTCAE) v4.03.

All safety analyses will be conducted on the SAF population.

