12.2 Adverse Events

Adverse events will be coded according to MedDRA dictionary version 10.

Symptoms and signs of exacerbation or worsening of the patient's primary disease will be captured as AEs.

A treatment emergent adverse event (TEAE) is defined as an AE occurring during or after administration of first dose of study drug, or any event after the first dose of study drug considered study drug-related regardless of event start date, or any worsening in intensity or event considered drug related by the investigator of a pre-existing medical condition/AE with onset after the start of study drug, and until Post-Treatment Safety Assessment visit (28 days after the last INXN-1001 dose per patient). AEs with unknown start date/time will be assumed to be treatment-emergent

unless the end date/time is known to be before start of study drug. AEs with onset after the completion of screening but prior to the start of study drug will be considered non-treatment emergent.

An overall AE summary will be presented for all AEs and the pre-defined subsets of events below:

- Any AEs
- Any TEAE events
- Any drug-related AEs
- Any CTC Grade 3 or greater AEs
- Any CTC Grade 3 or greater drug-related AEs
- Any AEs leading to death
- Any drug-related AEs leading to death
- Any serious AEs (SAEs)
- Any drug-related serious AEs
- Any AEs leading to discontinuation
- Any drug-related AEs leading to discontinuation
- Any dose limiting toxicities

Related is defined as 'possibly related' or 'related' to treatment in the opinion of the investigator.

Both number of events and number of patients will be tabulated. For patients, percentages will be calculated from the total number of patients per INXN-1001 dose cohort in each phase and group (for phase II only).

Summaries of TEAEs, drug-related adverse events, SAEs, drug-related SAEs, AEs with CTC grade ≥ 3 , drug-related AEs with CTC grade ≥ 3 and AEs leading to discontinuation will be tabulated by MedDRA System Organ Class (SOC) and specific AE preferred Term (PT) sorted by decreasing frequency within SOC. Both number of events and number of patients will be tabulated. For patients, percentages will be calculated from the total number of patients per INXN-1001 dose group.

All AEs, TEAEs, SAEs, drug-related adverse events, adverse events leading to discontinuation of study medication and adverse events leading to death will be listed.

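### The SAP's DLT percentage covers all treated patients and all cycles, while the protocol judges tolerability on first-cycle DLTs in cohorts that complete Cycle 1

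*SAP*

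**What the plan says.** **SAP.** Section 12.2 includes "Any dose limiting toxicities" among the rows of the overall adverse event summary and states that "percentages will be calculated from the total number of patients per INXN-1001 dose cohort", within each phase and Phase II group. No cycle limit is attached to the row. Section 12.0 adds: "All safety analyses will be conducted on the SAF population". Section 8.1 defines that population as "all patients who receive at least one INXN-1001 capsule", or at least one INXN-2001 injection if that came first. Section 8.0 says: "For the analysis, two populations will be used". These are SAF and the Activity Evaluable Population. There is no set of patients evaluable for DLT.

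**Protocol.** Section 6.2.4 treats a dose in the escalation part, or in the first Phase II group, as above the MTD under this condition: "If DLTs have been observed in >1 of the 3-6 subjects in a cohort during the first treatment cycle". For Group 2 the same count of 3 to 6 subjects in the first cycle applies, with a different consequence: the Safety Review Committee (SRC) convenes and the cohort is expanded by 3. Section 6.2.5 sets the MTD at no more than 1 in 6 subjects with a DLT (< 33%), again in the first cycle. It lets the SRC also consider later events that meet the DLT criteria. Under 7.4, subjects withdrawn before finishing Cycle 1 dosing for reasons other than toxicity "may be replaced so that a full cohort of subjects completes Cycle 1 safety evaluations". The synopsis plans "approximately 15 subjects enrolled in Phase II at a single dose level at or below the MTD".

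**The concern.** The protocol's tolerability rule rests on first-cycle events in a cohort that has been through Cycle 1. The SAP's DLT row uses a wider set on both sides of the fraction. An event meeting the DLT definition in Cycle 2 or later can enter the numerator. A patient who took one capsule, left for an unrelated reason and was replaced stays in the denominator.

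Safety and tolerability is the primary objective, and informing the choice of INXN-1001 dose and regimen is the first secondary objective. SAP 4.4 says DLTs led to both dose reductions in Phase II. A reader of the study report will naturally set the printed DLT percentage against the protocol's < 33%, but the two figures are not built on the same basis.

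**Working it through.** **Inputs.** MTD limit: at most 1 in 6, < 33%, first cycle (Protocol 6.2.5). Patients treated: 3, 3, 3 and 4 in Phase I; 4, 4, 3 and 2 in Phase II (SAP 1.0). DLT counts per cohort and numbers replaced are not given, so the counts in steps 3 and 4 are assumptions.

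**1. The plan's own figures.** 1/6 = 16.7%, which is below 33%; 2/6 = 33.3%, which is not. The limit agrees with itself at 6 subjects. The treated counts add up: 3 + 3 + 3 + 4 = 13 and 4 + 4 + 3 + 2 = 13, matching SAP 6.1.

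**2. The two bases side by side.**

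| | Protocol decision basis (6.2.4, 6.2.5, 7.4) | SAP DLT row (8.1, 12.0, 12.2) |
|---|---|---|
| Numerator | Subjects with a DLT in Cycle 1 | Patients with a DLT in any cycle |
| Denominator | Cohort filled, by replacement if needed, with subjects completing Cycle 1 safety evaluations | All patients with at least one capsule or injection |

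**3. Denominator alone.** Assume one replaced patient without a DLT.
- Six evaluable, 2 DLTs: 2/6 = 33.3% becomes 2/(6 + 1) = 2/7 = 28.6%, which reads as below 33% when the decision basis is not.
- Three evaluable, 1 DLT: 1/3 = 33.3% becomes 1/(3 + 1) = 1/4 = 25.0%.

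**4. Numerator as well.** Assume one further patient has a first DLT after Cycle 1.
- Three evaluable, none replaced, no Cycle 1 DLT: 0/3 = 0% becomes 1/3 = 33.3%.
- Three evaluable, one replaced, 1 Cycle 1 DLT: 1/3 = 33.3% becomes (1 + 1)/(3 + 1) = 2/4 = 50.0%.

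The printed rate can therefore fall below or rise above the decision basis.

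**5. Secondary point: counting beyond 6 subjects.** About 15 Phase II subjects in two groups puts at least 8 in one group (15/2 = 7.5), so the planned numbers go beyond the 3 to 6 for which 6.2.4 is worded. At 6 subjects, the phrases >1, 1 in 6 and < 33% all tolerate exactly one DLT. Above 6 they no longer coincide. At 15, for illustration, one-sixth allows 2 (15/6 = 2.5), while < 33% allows 4 (4/15 = 26.7%; 5/15 = 33.3%). The documents do not say how to count there. In the event, no Phase II regimen had more than 4 patients.

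**The case against.** Much of the case on the other side stands.

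- **The row drives no dose decision.** The SAP describes the final analysis and already reports the treated numbers in the past tense. The SRC acted during the trial on counts, and an extra patient in a denominator does not turn two DLTs into one. A reader might infer that the SAP row distorted the MTD or the dose reductions; the documents do not support that.
- **No replacement is documented.** A reader might take the three cohorts of 4 (Phase I 160 mg QD, Phase II 160 mg QD and QOD) as three patients plus one replacement. Appendix 5 allows up to 3 additional Phase I subjects after one DLT in three, and the Phase II groups were formed by amendment rather than in threes. The cohort sizes prove nothing. Section 7.4 does not call such subjects non-evaluable either; that is an inference from its stated purpose.
- **The bias is not one-way.** A reader might conclude that the SAP rate favors the dose. Step 4 shows it need not.
- **SAF is the normal denominator, and much of the information is already listed.** Protocol 10.3.2 assigns safety data to the Safety Population. SAP 12.1 lists cycles started and completed, reason for discontinuation and DLT status by patient. With 26 patients, a Cycle 1 figure could largely be rebuilt by hand. That makes the change cheap, but does not make the printed percentage the right one to compare with 6.2.5.
- **Beyond 6 subjects.** A reader might carry >1 to 15 subjects and find that two or more DLTs occur with probability 45% or 83% at true rates of 10% or 20%. The protocol words the rule only for 3 to 6 subjects, and the 15 span two regimens, so this tests a rule it does not state. Nor is control absent: the SRC may review at any time and may recommend a Group 2 reduction after one or more DLTs, and 6.2.7 covers Grade 4 toxicity and drug-related death. These provisions give discretion or address other events; none says how DLTs are counted above 6.

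**Conclusion.** The point holds as a reporting gap. The DLT percentage in SAP 12.2 does not share the protocol's first-cycle basis in numerator or denominator, and no population in the SAP can put it there. Its actual size cannot be found from the documents, which give neither DLT counts per cohort nor any replacement. In cohorts this small one patient moves the figure materially: 33.3% to 28.6% with six evaluable, or 33.3% to 25.0% with three, each assuming one replaced patient without a DLT. Later-cycle DLTs would move it upward. What is affected is the reported tolerability and the dose and regimen conclusions drawn from it, not the SRC decisions already made.

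The protocol's silence on counting beyond 6 subjects is a wording inconsistency among 6.2.4, 6.2.5 and the planned 15. It now matters for interpretation only, since no cohort in the SAP exceeded 4.

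**What to change.** **SAP.** Define a DLT-evaluable set: patients with a DLT in Cycle 1, or who completed Cycle 1 dosing and its observation period without one. Keep the SAF row and add beside it, per regimen: number treated, number non-evaluable or replaced with the reason for each, number evaluable, and Cycle 1 DLTs as a count and percentage of the evaluable. Show DLTs arising after Cycle 1 separately. Giving reasons matters because a patient who stops in Cycle 1 for toxicity short of a DLT would be non-evaluable here, yet 7.4 does not provide for replacing that patient.

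**Protocol or study report.** The sponsor and SRC should reconcile 6.2.4 (3 to 6 subjects), 6.2.5 (1 in 6, < 33%) and the approximately 15 Phase II subjects planned at one dose level, and state how DLTs were to be counted beyond 6. No threshold is proposed here.

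**Cost.** One more population, one small table and one clarifying statement. No extra patients are needed, and the patient-level inputs are largely those SAP 12.1 already lists, with event dates needed to separate Cycle 1 DLTs from later ones.

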15.1 List of Tables

| Table Number | Table Title | Population |
|----------------|--|-------------------------------|
| Table 14.1.1 | Patient Disposition | Safety Population |
| Table 14.1.2 | Protocol Deviations | Safety Population |
| Table 14.1.3 | Demography | Safety Population |
| Table 14.1.4 | Medical History | Safety Population |
| Table 14.1.5 | Oncology History | Safety Population |
| Table 14.1.6 | Oncology History – Time Since Diagnosis, Disease Status and Staging | Safety Population |
| Table 14.1.7 | Previous Medications | Safety Population |
| Table 14.1.8 | Concomitant Medications | Safety Population |
| Table 14.1.9 | Prior Cancer Treatment | Safety Population |
| Table 14.2.1 | Best Overall Response | Activity Evaluable Population |
| Table 14.2.2 | Progression-free Survival (Kaplan-Meier Analysis) | Activity Evaluable Population |
| Table 14.3.1 | Exposure | Safety Population |
| Table 14.3.2.1 | Overall Adverse Event Summary | Safety Population |
| Table 14.3.2.2 | Adverse Events by System Organ Class and Preferred Term | Safety Population |
| Table 14.3.2.3 | Treatment Emergent Adverse Events by System Organ Class and Preferred Term | Safety Population |

| Table Number | Table Title | Population |
|-----------------|---|-------------------|
| Table 14.3.2.4 | Drug-Related Treatment Emergent Adverse Events by System Organ Class and Preferred Term | Safety Population |
| Table 14.3.2.5 | Serious Adverse Events by System Organ Class and Preferred Term | Safety Population |
| Table 14.3.2.6 | Drug-Related Serious Adverse Events by System Organ Class, Preferred Term | Safety Population |
| Table 14.3.2.7 | CTC Grade 3 or greater Adverse Events by System Organ Class, Preferred Term | Safety Population |
| Table 14.3.2.8 | Drug-Related CTC Grade 3 or Greater Adverse Events by System Organ Class and Preferred Term | Safety Population |
| Table 14.3.2.9 | Adverse Events Leading to Discontinuation by System Organ Class and Preferred Term | Safety Population |
| Table 14.3.2.10 | Summary of Injection Site Reactions | Safety Population |
| Table 14.3.2.11 | Summary of Injection Site Reactions by Type and Severity | Safety Population |
| Table 14.3.2.12 | Summary of Injection Site Reactions by Type and Relationship | Safety Population |
| Table 14.3.3.1 | Shift from Baseline to Worst Post-Baseline Value (Low/High) for Clinical Chemistry Parameters | Safety Population |

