15.3 List of Listings

Listings will be sorted by patient number within Phase, group (for Phase II patients) and dose cohort.

| Listing Number | Listing Title | Population |
|-----------------------|---|-------------------|
| Listing 16.2.1.1 | Patient Disposition | Safety Population |
| Listing 16.2.1.2 | Inclusion and Exclusion Criteria | Safety Population |
| Listing 16.2.1.3 | Eligibility | Safety Population |
| Listing 16.2.2 | Protocol Deviations | Safety Population |
| Listing 16.2.3 | Population Allocation | Safety Population |
| Listing 16.2.4.1 | Demography and Baseline Characteristics | Safety Population |
| Listing 16.2.4.2 | Medical History | Safety Population |
| Listing 16.2.4.3 | Oncology History | Safety Population |
| Listing 16.2.4.4 | Prior Cancer Therapy | Safety Population |
| Listing 16.2.4.5 | Prior Medications | Safety Population |
| Listing 16.2.4.6 | Concomitant Medications | Safety Population |
| Listing 16.2.5.1 | Study Drug Administration | Safety Population |
| Listing 16.2.5.2 | Drug Dosing Schedule | Safety Population |
| Listing 16.2.5.3 | Overall Study Drug Exposure | Safety Population |
| Listing 16.2.5.4 | Pharmacokinetic Sampling | Safety Population |
| Listing 16.2.6.1 | Tumor Assessments | Safety Population |
| Listing 16.2.6.2 | Overall Tumor Assessments | Safety Population |
| Listing 16.2.6.3 | Best Overall Response and Progression-free Survival | Safety Population |
| Listing 16.2.6.4 | PBMC | Safety Population |
| Listing 16.2.6.5 | Serum Antibody Responses | Safety Population |
| Listing 16.2.6.6 | Cytokine Profiling Responses | Safety Population |
| Listing 16.2.6.7 | Serum Tryptase Responses | Safety Population |
| Listing 16.2.6.8 | T cells | Safety Population |
| Listing 16.2.6.9 | NK cells | Safety Population |
| Listing 16.2.6.10 | T-regulatory (Tregs) | Safety Population |
| Listing 16.2.6.11 | Adenoviral Vector Shedding | Safety Population |
| Listing 16.2.7.1 | Adverse Events | Safety Population |
| Listing 16.2.7.2 | Treatment Emergent Adverse Events | Safety Population |

| Listing Number | Listing Title | Population |
|-----------------------|---|-------------------|
| Listing 16.2.7.3 | Treatment Emergent Serious Adverse Events | Safety Population |
| Listing 16.2.7.4 | Treatment Emergent Adverse Events Related to Study Drug | Safety Population |
| Listing 16.2.7.5 | Treatment Emergent Adverse Events Leading to Withdrawal | Safety Population |

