| Listing 16.2.7.6 | Treatment Emergent Adverse Events Leading to Death | Safety Population |
| Listing 16.2.7.8 | Injection Reaction | Safety Population |
| Listing 16.2.8.1 | Laboratory Reference Ranges | Safety Population |
| Listing 16.2.8.2 | Clinical Chemistry | Safety Population |
| Listing 16.2.8.3 | Hematology | Safety Population |
| Listing 16.2.8.4 | Urinalysis Data | Safety Population |
| Listing 16.2.8.5 | Pregnancy Test | Safety Population |
| Listing 16.2.9 | Vital Signs | Safety Population |
| Listing 16.2.10 | ECG Data | Safety Population |
| Listing 16.2.11 | ECOG Status | Safety Population |
| Listing 16.2.12 | Physical Examination | Safety Population |
| Listing 16.2.13 | Visit Dates | Safety Population |
| Listing 16.2.14 | Photo Catalog | Safety Population |
| Listing 16.2.15 | Waiver | Safety Population |
| Listing 16.2.16 | Adenoviral Vector Shedding | Safety Population |

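### SAE, Grade 3+ and discontinuation AE tables count events by dose cohort with no first-dose limit, and the matching listings have a narrower, treatment-emergent scope

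*SAP*

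**What the plan says.** **Collection.** Protocol 8.4.2.6 and 9.3 put AEs and SAEs on the AE page from consent to the Post-Treatment Safety Assessment. Protocol 9.4 collects SAEs and deaths, related or not, from consent to 30 days after last dose.

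**Protocol analysis.** Protocol 10.3.2 places all AEs in by-subject listings and says that treatment-emergent events are the ones to be tabulated. It also says that deaths, SAEs and AEs causing study discontinuation will be listed, with no treatment-emergent limit. Protocol 10.4 expects the SAP to indicate departures from the protocol's analyses.

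**SAP definition.** SAP 12.2 defines a TEAE and adds: "AEs with onset after the completion of screening but prior to the start of study drug will be considered non-treatment emergent".

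**SAP tables.** The same section announces "Summaries of TEAEs, drug-related adverse events, SAEs, drug-related SAEs, AEs with CTC grade" 3 or above, and further categories, with patient percentages by INXN-1001 dose. In SAP 15.1 the drug-related table is "Drug-Related Treatment Emergent Adverse Events by System Organ Class and Preferred Term", but Table 14.3.2.5 is "Serious Adverse Events by System Organ Class and Preferred Term" and Table 14.3.2.7 is "CTC Grade 3 or greater Adverse Events by System Organ Class, Preferred Term". Table 14.3.2.9, for discontinuation, also has no treatment-emergent qualifier.

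**SAP listings.** SAP 12.2 says: "All AEs, TEAEs, SAEs, drug-related adverse events, adverse events leading to discontinuation of study medication and adverse events leading to death will be listed". In SAP 15.3, however, Listing 16.2.7.3 is "Treatment Emergent Serious Adverse Events" and Listing 16.2.7.6 is "Treatment Emergent Adverse Events Leading to Death". Listing 16.2.7.5, for withdrawals, is restricted in the same way. Listing 16.2.7.1 covers all AEs without restriction.

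**The concern.** Safety is the primary objective, the analysis is purely descriptive, and results are laid out by the INXN-1001 dose received on Cycle 1 Day 1. In that layout, a count in a cohort column reads as something that happened on that dose. An event that began between consent and first dose did not. The interval is real: Protocol Table 2 puts consent between Day -28 and Day -7 and punch biopsies at Day -6 to -2, so an invasive study procedure precedes dosing. The Safety Population restricts which patients are counted, not which of their events.

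The SAP recognises the distinction and applies it to some outputs. For SAEs and Grade 3+ AEs, the outputs a safety reader turns to first, no planned table gives the on-treatment count.

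The second issue is traceability. SAP 9.1 requires each table to name its supporting listing. If the SAE table covers all SAEs and the SAE listing covers only treatment-emergent ones, a count in the table may have no matching line in the listing.

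**Working it through.** **Step 1. Scope of each output, side by side (SAP 12.2, 15.1, 15.3).**

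| Event type | Table | First-dose limit in table? | Listing | Treatment-emergent limit in listing? |
|---|---|---|---|---|
| All AEs | 14.3.2.2, companion 14.3.2.3 | No; yes in companion | 16.2.7.1, 16.2.7.2 | No; yes |
| Drug-related AEs | 14.3.2.4 | Yes | 16.2.7.4 | Yes |
| SAEs | 14.3.2.5 and a row of 14.3.2.1 | No, no companion | 16.2.7.3 | Yes |
| Grade 3+ AEs | 14.3.2.7 and a row of 14.3.2.1 | No, no companion | none dedicated | n/a |
| AEs leading to discontinuation | 14.3.2.9 and a row of 14.3.2.1 | No, no companion | 16.2.7.5 | Yes |
| AEs leading to death | row of 14.3.2.1 only | No | 16.2.7.6 | Yes |

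Since some titles carry the qualifier and others do not, its absence cannot be read as implied. The SAP sentence on pre-dose events speaks of onset after screening is complete. An event with onset during screening does not meet the onset limb of the TEAE definition either, so both kinds are non-treatment-emergent unless they later worsen or are judged drug-related.

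**Step 2. Denominators.** SAP 1.0 gives Phase I cohorts of 3, 3, 3 and 4, and Phase II cohorts of 4 (160 mg QD), 4 (160 mg QOD), 3 (120 mg QOD) and 2 (80 mg QOD).

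- Phase I: 3 + 3 + 3 + 4 = 13. Phase II: 4 + 4 + 3 + 2 = 13. Both match SAP 6.1.
- Three cohorts have n = 4, four have n = 3 and one has n = 2.
- Group 2: 4 + 3 + 2 = 9.

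**Step 3. Weight of one patient whose only qualifying event began before first dose**, 100/n:

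- n = 4: 25.0 points
- n = 3: 33.3 points
- n = 2: 50.0 points
- Group 2, n = 9: 11.1 points
- a phase's Overall column, n = 13: 7.7 points

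If the same patient also has a qualifying event after first dose, the patient percentage is unchanged and only the event count rises.

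**Step 4. The late end.** AE-page recording stops at the Post-Treatment Safety Assessment and SAE reporting runs to day 30. Protocol Table 2, footnote 28, sets the visit at 28 ± 3 days after last dose, or at early withdrawal.

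- Visit on day 25: 30 − 25 = 5 days uncovered by the AE page.
- Visit on day 28: 30 − 28 = 2 days.
- Visit on day 31: none.
- Visit on the day of last dose, the extreme at early withdrawal: 30 − 0 = 30 days.

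An unrelated SAE or death in that gap is collected as a report, but it reaches Table 14.3.2.5 or Listing 16.2.7.1 only if it is also entered as an AE.

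**The case against.** The strongest reply is that this is a labelled choice. The tables are titled as SAEs and Grade 3+ AEs, nothing all-event is presented as treatment-emergent, and TEAEs have their own row and table. Protocol 10.3.2 bases safety on AEs and SAEs generally and does not forbid all-event tables. This stands as far as it goes. A reader might infer that the SAP breaches the protocol, and the documents do not support that. What they show is a difference that SAP 14.0 does not mention.

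Second, Listing 16.2.7.1 holds every SAE, discontinuation and fatal event entered as an AE, and SAP 12.2 can be read as satisfied by it. That also stands. A reader might infer that pre-dose SAEs vanish from the report, but they do not. The problem is that the dedicated listings do not match the corresponding table counts.

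Third, the 25 to 50 points are the weight of any single event in a cohort of 2 to 4, and no pre-dose event is known. This is correct and limits the severity. It does not justify leaving the first-dose limit off the primary safety tables.

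Fourth, the late gap is mainly a collection matter: if a late SAE is not on the AE page, no listing title restores it. That is right, and it means the remedy must include data reconciliation.

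**Conclusion.** The concern holds, and it is minor. As written, the SAE, Grade 3+ and discontinuation tables and their summary rows can credit an event that began before dosing to an INXN-1001 dose cohort, and no treatment-emergent SAE or Grade 3+ table is planned. The treatment-emergent listings for SAEs, withdrawals and deaths are narrower than the corresponding tables or summary rows and than the SAP 12.2 text.

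The possible size is 25 to 50 points in a cohort column and about 8 in a phase's Overall column. This assumes a dosed patient whose only event of that type began between consent and first dose. The documents give no rate for such events, so their likelihood cannot be stated.

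A reader might also infer that the dose reductions or the tolerability conclusions could be distorted. The documents do not support that. SAP 4.4 attributes the reductions to DLTs, which Protocol 6.2.4 defines as injection reactions or study-drug-related events. The drug-related SAE and Grade 3+ tables (14.3.2.6 and 14.3.2.8) are little affected, because a pre-dose event should rarely be judged drug-related. No inferential analysis is planned.

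**What to change.** 1. **Tables.** Limit Tables 14.3.2.5, 14.3.2.7 and 14.3.2.9 and the matching rows of Table 14.3.2.1 to events meeting the start-side limbs of the SAP's own TEAE definition: onset on or after first dose, worsening after first dose, or judged drug-related whatever the start date. Keeping the drug-related limb means that every event in Table 14.3.2.6 is also in Table 14.3.2.5. Do not apply the end of the TEAE window, so that SAEs and deaths recorded after the Post-Treatment Safety Assessment stay in. Footnote this scope. Alternatively, keep the all-event tables and add treatment-emergent companions, as is done with 14.3.2.2 and 14.3.2.3.
2. **Listings.** Make Listings 16.2.7.3, 16.2.7.5 and 16.2.7.6 cover all recorded SAEs, discontinuations and deaths, with one flag for pre-dose, treatment-emergent or post-visit. Each table count can then be traced to flagged lines.
3. **Reconciliation.** Before lock, reconcile SAE reports to day 30 (Protocol 9.4) with the AE data.
4. **Record.** Note any remaining difference from Protocol 10.3.2 in SAP 14.0.

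Items 1, 2 and 4 cost SAP wording and output specifications. Item 3 is a small data-management task. None needs further data from patients.
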